13 N/A  
14

### 15 **B5.7.2 Drugs**

16 N/A  
17

18 **B5.7.2.1 FDA-approved and used in accordance with the approved labeling**

19 N/A  
20

21 **B5.7.2.2 FDA-approved and used in a manner not in accordance with its approved labeling**

22 N/A  
23

24 **B5.7.2.3 Any drug not approved by the FDA**

25 N/A  
26

## 27 **B5.8 Statistical Analysis**

### 28 **B5.8.1 Sample Size Estimation**

29  
30  
31 Statistical power and sample size were determined from the effect size of exogenous  
32 carbohydrate oxidation ( $-14 \pm 8$  g/40-min exercise) that we previously observed at HA compared  
33 to SL. Using this information the sample size necessary to determine statistical significance  
34 between intervention arms is 7, with an alpha of 0.05 and 80% power. To account for greater  
35 variance in the response to altitude between volunteers and increased study power to 90%, 10  
36 volunteers will be enrolled to complete this investigation. Based on our previous studies we  
37 request to consent 30 individuals to complete 10.  
38

### 39 **B5.8.2 Data analysis**

40  
41 Statistical analyses will be conducted using either SPSS (IBM Corp. Armonk, NY), SAS 9.3 (SAS  
42 Institute Inc., Carey, NC), or equivalent. Common descriptive statistics will be used to describe  
43 volunteer characteristics. Shapiro-Wilk tests will be used to determine normality of data. Paired t-  
44 test will be performed to determine main effects of phase (SL versus HA) for glucose turnover and  
45 glucose oxidation. Mixed model repeated measures ANOVA will be performed to determine main  
46 effects of time (baseline versus post-exercise), phase (SL versus HA) and time-by-phase  
47 interactions for glucose and insulin concentrations, GLUT4 translocation, glycogen, mRNA and  
48 microRNA, Western blots and enzyme activity. If interactions are significant, appropriate post-  
49 hoc correction will be used to examine these relationships. Correlation coefficients and multiple  
50 regression analysis will be used to evaluate relationships between study outcome measures. The  
51 alpha level will be adjusted for multiple comparisons, with the level for statistical significance set  
52 at  $P < 0.05$ .  
53

---

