## 5 **B5. RESEARCH PLAN**

### 6 **B5.1 Research Design**

7  
8  
9 This study will be a randomized crossover control trial.

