#### 25 **B5.2.2 Number of Subjects, Records, and/or Specimens**

26  
27 We estimate that 30 individuals will require screening in order to complete testing on the 10 volunteers  
28 necessary to reach statistical power. All screening will stop once complete data has been collected on  
29 10 volunteers. Records and specimen collection are described in the Research Procedures and Data  
30 Collection sections. During briefings and the consenting process potential volunteers will be informed  
31 that even though they may be eligible and want to participate, if we are able to obtain enough data from  
32 preceding subjects, they may not ultimately be tested.  
33

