### B5.3 Research Procedures

#### Study Design

This randomized crossover study will examine substrate metabolic responses to ingesting supplemental carbohydrate during steady-state aerobic-type exercise at sea level (SL) and following acute (~5 h) exposure to HA (4,300 m) conditions in 10 healthy, recreationally active adults between the ages of 18-39 yrs (**Table 1**). Following a 48-hr muscle glycogen normalization period, volunteers will complete 80-min of metabolically-matched, steady-state aerobic exercise on a treadmill, and consume 145 g of glucose ( $1.8 \text{ g}\cdot\text{min}^{-1}$ ) at SL and HA. Treadmill exercise will be performed at the same absolute workload, with speed and grade being the same at SL and HA to induce the same absolute workload between phases. SL and HA trials will occur in the USARIEM hypobaric chamber and will be separated by a minimum 7-d washout period between each protocol day. 6-6-[ $^2\text{H}_2$ ] glucose will be used as a tracer to assess glucose turnover. Indirect calorimetry, breath sampling for  $^{13}\text{C}/^{12}\text{C}$  expired in  $\text{CO}_2$ , and urine collections will be used to determine carbohydrate, fat, and protein oxidation during exercise at SL and HA. Serial blood draws will be collected during each trial to assess endocrine and circulating substrate responses to exercise, carbohydrate, and hypoxia. Muscle biopsies will be collected before and after steady-state exercise to examine intramuscular glucose transport expression and translocation, glycogen status, and activity enzyme intermediates in aerobic and anaerobic energy metabolism.

1

Study Day	SV	1	2	3	4	5	6	7	8	9	10	11	12	13	14	15
Medical Screening	X															
Body Composition		X														
Height		X														
Weight		X						X							X	
Fitness Assessment		X	X													
Blood Sampling								X							X	
Exercise Practice Sessions				X	X											
Muscle Biopsies								X							X	
Carbohydrate Depletion Exercise						X						X				
Steady-State Exercise								X							X	
Study Diet						X	X					X	X			
Carbohydrate Tracer Study								X							X	
Post Biopsy Follow-Up									X							X

2

3

4

**Table 1.** Study Timeline

5

6

Note that this is a potential timeline, specific study days and length of time to complete the study may be dependent on volunteer’s availability, so total time commitment may be longer.

7

8

9

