#### 8 9 Steady-State Treadmill Exercise Prescription

10 Results from  $\dot{V}O_{2peak}$  assessment will be used to prescribe steady-state treadmill exercise for protocol  
11 days. At SL and HA volunteers will complete 80-min of steady-state exercise on a treadmill at  $55 \pm 5\%$   
12 of their  $\dot{V}O_{2peak}$  determined at HA, performing the same absolute work under both study conditions. The  
13 speed and grade of the treadmill will be determined using the ACSM metabolic equation for walking  
14 based on desired  $\dot{V}O_2$  (22). Prior to the protocol day, participants will perform a practice session of the  
15 treadmill exercise to confirm the prescribed speed and grade are appropriate to induce target  $\dot{V}O_2$ . The  
16 speed and grade determined during the practice session will be used at SL and HA to induce the same  
17 absolute  $\dot{V}O_2$  between phases.

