**Exercise Protocol Day**

Two catheters will be placed into the lower arm (one in each arm). One arm will be used for infusion of 6,6-[H2] glucose tracer and the other will be used for blood sampling under resting and exercise conditions. Following an initial blood and breath sample collection to determine background enrichments, a primed, continuous infusion of 6,6-[H2] glucose will begin (prime, 82.2 μmol·kg; continuous rate, 0.78 μmol·kg·min, **Figure 4**) (24, 25). Volunteers will complete 80-min of steady-state exercise on a treadmill at 55 ± 5% of their VO2peak determined at HA, performing the same absolute work under both study conditions. V̇O2, V̇CO2, HR, and SaO2 will be measured at approximately 320, 330, 340, 360, 380, and 395 min. During exercise volunteers will consume a CHO beverage at 1.8 g·min to examine the impact of altitude exposure on exogenous carbohydrate oxidation efficiency. Drinks will contain 145 g glucose, with a total volume of 1450 mL. The drink will be consumed in four boluses throughout the 80-min of steady-state exercise (320, 340, 360, and 380-min). The first bolus will be 550 mL, with the remaining three being 300 mL. The CHO beverage consumed during exercise will be enriched with 200 mg U-C-glucose (Cambridge Isotope Laboratory, Andover, MA, USA) to increase the isotopic enrichment well above natural levels and optimize the measurement of exogenous carbohydrate oxidation. Before exercise, during the HA phase, volunteers will be exposed to hypobaric hypoxic conditions for 5-hrs to mimic our previous investigation. Muscle samples will be obtained using percutaneous muscle biopsy, taken from the vastus lateralis using a 5-mm Bergstrom needle with manual suction while the volunteer is under local anesthesia (1% lidocaine) according to the approved USARIEM SOP (26, 27). Muscle samples will be collected before (300 min) and immediately (420 min) after 80-min of steady state exercise during both the SL and HA protocol study days. The two muscle biopsy collections will occur from one incision each protocol day. Following a minimum 7-d washout period, volunteers will return to the laboratory to complete the second arm of the investigation. A total of four muscle biopsies will be conducted per volunteer, two per protocol day, with one incision made on each leg.

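### The order of the sea-level and altitude visits is randomised, but no planned analysis includes a term for visit order

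*Combined protocol and SAP*

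**What the plan says.** Section B5.1 states: "This study will be a randomized crossover control trial". The Study Design text in B5.3 also calls it a randomised crossover. Each volunteer is tested once at sea level (SL) and once at high altitude (HA). After a washout of at least 7 days, "volunteers will return to the laboratory to complete the second arm of the investigation".

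Section B5.8.2 analyses glucose turnover and oxidation, which include the outcome used for sample size, with a paired t-"test will be performed to determine main effects of phase (SL versus HA) for glucose turnover and" glucose oxidation. The other listed outcomes get a mixed-model repeated-measures ANOVA for "effects of time (baseline versus post-exercise), phase (SL versus HA) and time-by-phase" interactions. The section itself defines phase as the SL/HA condition and time as before versus after exercise, so neither means visit order. No period or sequence term, and no check for an order effect, appears in the text supplied.

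On numbers, B5.2.2 says: "All screening will stop once complete data has been collected on" 10 volunteers. The text supplied gives no allocation method and no rule that keeps completers balanced by sequence.

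**The concern.** Randomising the order makes visit order a design factor, and a crossover analysis would normally carry it. Volunteers arrive at visit 2 having already done one full protocol day, two biopsies and a depletion ride to exhaustion, so a difference between visits cannot be ruled out in advance. None is claimed here.

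If there is one, the paired t-test handles it in one of two ways:

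- **Equal sequences:** the period effect cancels from the mean difference but inflates its variance. The test becomes conservative and the interval too wide.
- **Unequal sequences:** part of the period effect stays in the SL-HA estimate, in either direction.

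The second case matters because the stated objective is to confirm an earlier result, so the size of the estimate counts as well as its significance. In the mixed models only the phase main effect is exposed. An additive visit effect cancels from the time-by-phase interaction.

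**Working it through.** **Inputs.** Section B5.8.1 gives an effect of −14 ± 8 "g/40-min exercise) that we previously observed at HA compared" with SL, alpha 0.05, N = 7 for 80% power, and N = 10 for 90%. I read 8 g as the SD of the within-volunteer HA−SL difference and alpha as two-sided; the section states neither. The period effect π (visit 2 minus visit 1) is not in the documents, so 0, 2, 4 and 8 g are assumed. The sequence split is not given either, so 5:5, 6:4 and 7:3 are shown.

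**The plan's own figure.** A paired t-test with difference 14 and SD 8 reaches 82.8% power at n = 5 and 99.8% at n = 10. The stated 7 comes back from an independent two-sample calculation (78.0% at 6 per arm, 85.2% at 7 per arm). It is therefore uncertain which SD the 8 g is.

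**Algebra.** Let τ be the true HA−SL effect. The expected difference is τ + π for SL-first volunteers and τ − π for HA-first volunteers. With n1 SL-first and n2 HA-first volunteers:

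- Bias of the paired mean, given the split = π(n1 − n2)/n. This is 0 at 5:5, 0.2π at 6:4 and 0.4π at 7:3.
- Expected variance used by the paired test = σ² + π² × 4n1n2/[n(n − 1)]. At 5:5 with π = 8 this is 64 + 64 × 100/90 = 135.1, an SD of 11.6 g instead of 8 g.
- Period-adjusted estimate = average of the two sequence means, with pooled variance on 8 df. It is unbiased at every split. At 5:5 it equals the paired mean, and only the standard error differs.

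**5:5 split** (simulated; half-width is the average 95% half-width)

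| π (g) | Paired half-width (g) | Adjusted half-width (g) | Paired type I error | Paired power, 14 g |
|---|---|---|---|---|
| 0 | 5.57 | 5.65 | 5% | 99.8% |
| 2 | 5.76 | 5.65 | 4% | 99.8% |
| 4 | 6.30 | 5.65 | 3% | 99.5% |
| 8 | 8.15 | 5.65 | 0.7% | 97.3% |

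Adjusted type I error is 5% and power 99.8% throughout. Adjustment gives the narrower interval once π exceeds about 1.4 g.

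**7:3 split** (adjusted bias 0, power 99%, type I error 5%)

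| π (g) | Paired bias (g) | Power, 14 g, bias opposing | Power, 14 g, bias reinforcing | Paired type I error |
|---|---|---|---|---|
| 2 | 0.8 | 99.5% | 99.9% | 5% |
| 4 | 1.6 | 98% | 99.9% | 6% |
| 8 | 3.2 | 84% | 99.9% | 6.4% |

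**A smaller effect.** For 7 g (half the planning effect, chosen for illustration) with π = 4 g, power at 5:5 is 60% paired and 68% adjusted. At 7:3 it is about 40% (opposing) or 80% (reinforcing) paired, and about 60% adjusted.

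**Mixed models.** With an additive 8 g visit effect at 7:3, the phase main effect is biased by 3.2 g and time-by-phase by 0.

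**Chance of imbalance.** If simple 1:1 randomisation were used (an assumption), Binomial(10, 0.5) gives 24.6% for exactly 5:5 and 34.4% for 7:3 or worse.

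**The case against.** The strongest reply is that no period effect is documented and the design works against one. The plan has a washout, practice sessions, a 48-hour glycogen normalisation with provided food, and a fixed workload: the "speed and grade determined during the practice session will be used at SL and HA to induce the same" absolute oxygen uptake. If the 46% fall in the Background and the 14 g in B5.8.1 come from the same data, the SL value is about 14/0.46 = 30 g. An 8 g shift would then be about 26% of it, which is large for two standardised visits. This stands. The 8 g rows are an outer bound, and the smaller values are the more useful guide. But these measures can only reduce a period effect; they do not adjust for it, and washout is aimed at carry-over.

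Second, the main comparison is robust. At 5:5 power never falls below 97%, and N = 10 would hold 90% power up to a difference SD of about 12.1 g. This also stands, and it is why the point concerns precision and the estimate more than significance.

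Third, adjustment is not always better. At 7:3 the paired mean squared error is 6.4 + 0.16π² against 64(1/7 + 1/3)/4 = 7.62 adjusted, so the paired estimate is more accurate until π is about 2.8 g. At 6:4 the crossover is about 2.6 g. This is correct. It argues for keeping the sequences balanced, where the two estimates coincide.

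Fourth, averaged over 1:1 randomisation the bias is zero. That is true, but the trial will report one realised split.

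Fifth, B5.8.2 lists the effects to be determined and does not say the mixed models exclude other terms. That is fair as a reading, but a term that is not named is not prespecified, and the paired t-test has no place for one.

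**Conclusion.** The concern holds. A randomised crossover is planned, and no stated analysis uses visit order. The direction of the consequences follows from algebra; their size depends on an unknown period effect. With n = 10 and a difference SD of 8 g, an assumed 4 g period effect at 5:5 costs about 0.65 g of half-width (6.30 versus 5.65 g). At 7:3 it shifts the estimate by 1.6 g. Below about 1.4 g at 5:5, leaving out the term does no harm. If 8 g is not the SD of differences, the half-widths, power and break-even values change, but the bias formula does not.

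This does not put the planned 14 g comparison in doubt. It is a worthwhile, inexpensive correction that matters most for the reported size of the effect, for outcomes with smaller effects, and for phase main effects in the mixed models.

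**What to change.** In B5.8.2:

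- **Glucose turnover and oxidation:** replace the paired t-test with a model that has fixed effects of condition (SL/HA) and period (visit 1/2) and a random volunteer effect. An equivalent form is the mean of the two sequence-specific HA−SL differences, or the intercept from regressing each volunteer's difference on sequence coded +1/−1. A 0/1 code would give one sequence's mean instead.
- **Mixed models:** add period as a fixed effect, to protect the phase main effect.
- **Allocation and reporting:** assign the two sequences in balanced blocks, state this in the protocol, and report the completed split.

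The cost is SAP wording and an allocation procedure, with no added volunteers or measurements. Trial number is already a field on the biopsy form in Appendix B.

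The statistical cost if there is no period effect is a half-width of 5.65 g at 5:5, 5.77 g at 6:4 and 6.17 g at 7:3, against 5.57 g paired (about 2%, 4% and 11% wider). For a 7 g effect, power goes from 69% to 68% at 5:5 and to about 60% at 7:3. Balanced blocks keep the cost near the low end, though dropouts could still leave the completers uneven.

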30 exogenous carbohydrate oxidation rates are achieved between 51-64% of  $\dot{V}O_{2max}$  (11). Therefore, in  
31 this previous study (2), it is possible that exogenous carbohydrate oxidation was already maximal  
32 during the normoxic exercise trials and could not increase any further during the hypoxic exercise. In a  
33 recent investigation, our laboratory sought to examine whether oxidation rates of exogenous glucose  
34 would differ during exercise performed at the same absolute intensity in normoxic and hypoxic  
35 conditions at exercise intensities eliciting less than maximal exogenous carbohydrate oxidation rates at  
36 HA. Findings from this study (unpublished) indicated that exogenous glucose oxidation diminished by  
37 46% from SL to HA when participants consumed 144 g carbohydrate while walking on a treadmill for  
38 80-min at a fixed absolute workload ( $\dot{V}O_2 = \sim 1.7 L \cdot min^{-1}$ ; 55%  $\dot{V}O_{2max}$  at HA; **Figure 1**). While  
39 exogenous glucose oxidation was lowered in our investigations, endogenous carbohydrate oxidation  
40 was numerically but not statistically higher at HA compared to SL. These data suggested that the  
41 body's ability to oxidize exogenous glucose during exercise may be compromised during acute HA  
42 exposure.

[figure not shown]
Figure 1: Carbohydrate oxidation

43  
44 Decreased insulin sensitivity is one potential mechanism for diminished ability to oxidize exogenous  
45 carbohydrate oxidation at HA (12-15). Concomitant with the suppression of exogenous carbohydrate  
46 oxidation in acute hypoxia, we also observed that blood glucose levels rose higher and remained  
47 elevated during exercise despite two to four fold higher insulin concentrations during HA exercise  
48 compared to SL (**Figure 2**). Under normal physiological conditions, elevated blood glucose levels  
49 stimulates a rise in circulating insulin to induce translocation of glucose transporter 4 (GLUT4), resulting  
50 in the uptake of glucose intake the cell. Several other investigations (12-15) have also observed this  
51 phenomenon of impaired insulin sensitivity upon acute exposure to HA in young healthy individuals.  
52 Therefore, it is possible that insulin resistance at HA may be a mechanism suppressing exogenous  
53 carbohydrate oxidation. However, little is known regarding alterations in intramuscular processes that

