### 31 B4. OBJECTIVES/SPECIFIC AIMS/RESEARCH QUESTIONS

#### 32 Objectives

33  
34  
35 Confirm results from our previous investigation that acute HA exposure decreased exogenous  
36 carbohydrate oxidation during steady-state aerobic exercise compared to SL, and explore if the  
37 mechanism inhibiting plasma glucose uptake is insulin dependent or independent.  
38  
39

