**B5.4 Data Collection**

*Blood Sampling*

Blood samples will be collected using intravenous access by a USARIEM credentialed phlebotomist on throughout protocol days under SL and HA conditions (**Figure 4**). Baseline blood sampling will occur after a 10-hr overnight fast. A total of 26 blood draws will be completed during this study taking 438 mL of blood sampled from each volunteer over the two protocol days (**Table 2**). Blood samples will be used for isotope analysis, assessment of nutrient status, hormone response, and circulating microRNA (**Table 3**).

**Table 2.** Total Volume of Blood Sampled for Protocol Days

Tube	Number of Tubes	Total Volume (mL)
7.5 mL Red Top Tube	8	60
4 mL Red Top Tube	8	32
4 mL Green Top Tube	16	64
1.2 mL Green Top Tube	16	20
6 mL Purple Top Tube	18	108
4 mL Purple Top Tube	28	112
2.6 mL Gray Top Tube	16	42
Total	110	438

**Table 3.** Blood Analytes

Analyte	Time Point (min)												
	120	180	210	240	260	280	300	320	340	360	380	400	420
Glucose 	X						X	X	X	X	X	X	X
Insulin 	X						X	X	X	X	X	X	X
Free fatty acids 	X						X	X	X	X	X	X	X
Lactate 	X						X	X	X	X	X	X	X
Glycerol 	X						X	X	X	X	X	X	X
Norepinephrine 	X						X	X	X	X	X	X	X
Epinephrine 	X						X	X	X	X	X	X	X
Hemoglobin 	X						X			X			X
Hematocrit 	X						X			X			X
 C-glucose 								X	X	X	X	X	
6,6-[  H 2 ] glucose 		X	X	X	X	X	X	X	X	X	X	X	X
c-miRNA *1	X						X			X			X
Exosomal miRNA 	X						X			X			X
PBMC +	X						X						X
Archive	X	X	X	X	X	X	X	X	X	X	X	X	X

\* Analytes: c-miRNA, circulating microRNA, +Peripheral blood mononuclear cell

Samples will be analyzed at USARIEM, Pennington Biomedical Research Center (Baton Rouge, LA) Metabolic Solutions (Nashua, NH), and The Center for Translational Research in Aging and Longevity (Little Rock, AR). All blood samples will be separated into plasma and serum through centrifugation,

1 aliquoted, and stored at  $-80^{\circ}\text{C}$  until analysis or shipment. Study samples will be collected and aliquoted  
2 at USARIEM and specific samples will be shipped on dry ice to Pennington Biomedical Research  

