#### 28 Plasma Glucose Turnover Calculations

29 For calculation of plasma glucose turnover the Steele equation with modifications for non-steady state  
30 will be used (28). Enrichment (E) will be expressed as mole percent excess (MPE); calculated as  
31  $(\text{TTR})/(1 + \text{TTR})$ , where TTR is the tracer to tracee ratio. Appropriate corrections for skewed  
32 abundance distribution and overlapping spectra will be made for the TTR of the glucose tracers, 6,6-  
33  $^{2}\text{H}_2$  glucose and U- $^{13}\text{C}$ -glucose (28). From these calculations, total glucose  $R_a$  will be comprised of  
34 rates of appearance of exogenous (i.e., ingested) glucose and of endogenous (i.e., hepatic glucose  
35 production and negligible renal glucose production or splanchnic glucose) glucose (28):  
36

$$37 \text{ Total glucose } R_a (\text{Total } R_a) = (F - ((pV \times ((C_2 + C_1) / 2) \times ((E_2 - E_1) / (t_2 - t_1)))) / ((E_2 + E_1) / 2)$$

$$38 \text{ Glucose } R_d = \text{Total } R_a - (pV (C_2 - C_1) / (t_2 - t_1))$$

$$39 \text{ Exogenous glucose } R_a (\text{Exo } R_a) = ((\text{Total } R_a + F) \times ((G_2 + GE_1) / 2) + (pV \times ((C_2 + C_1) / 2)) \times$$

$$40 ((G_2 - G_1) / (t_2 - t_1))) \text{ Endogenous glucose } R_a = \text{Total } R_a - \text{Exo } R_a$$

$$41 \text{ Metabolic Clearance Rate (MCR) = Glucose } R_d / ((C_2 + C_1) / 2)$$

42  
43 Where F represents the infusion rate of 6,6- $^{2}\text{H}_2$  glucose;  $pV$  is the effective volume of distribution for  
44 glucose,  $C_1$  and  $C_2$  are plasma glucose concentrations at  $t_1$  and  $t_2$ , respectively,  $E_1$  and  $E_2$  are plasma  
45 enrichments of 6,6- $^{2}\text{H}_2$  glucose at  $t_1$  and  $t_2$ , respectively, and  $E_d$  and  $E_p$  are tracer enrichments of U-  
46  $^{13}\text{C}$ -glucose from the test drink and plasma, respectively.  
47

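### The two-level time factor in B5.8.2 leaves insulin at 340, 360 and 380 min, during exercise, with no specified sea-level versus altitude test

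*Combined protocol and SAP*

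**What the plan says.** B5.8.2 (Data analysis) names two kinds of test for sea level (SL) against high altitude (HA). A paired t-test covers glucose turnover and glucose oxidation. A mixed-model repeated measures ANOVA covers "effects of time (baseline versus post-exercise), phase (SL versus HA) and time-by-phase" interactions. The ANOVA's outcome list opens with glucose and insulin concentrations and goes on to GLUT4 translocation, glycogen, mRNA and microRNA, Western blots and enzyme activity.

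The sampling differs between these outcomes:

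- **Muscle** (B5.3, Exercise Protocol Day): "Muscle samples will be collected before (300 min) and immediately (420 min) after 80-min of steady state exercise". That is two samples per protocol day.
- **Blood** (B5.4, Table 3): glucose and insulin at 120, 300, 320, 340, 360, 380, 400 and 420 min. That is eight samples per protocol day.

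The Study Design text in B5.3 says the serial draws are there to "assess endocrine and circulating substrate responses to exercise, carbohydrate, and hypoxia".

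**The concern.** A time factor with two levels can hold only two of the eight glucose and insulin draws. For insulin, the draws left out include those at the centre of the exercise bout, while glucose is being ingested.

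This bears on the second part of the objective in B4, which is to explore whether the "mechanism inhibiting plasma glucose uptake is insulin dependent or independent". The observation behind that question was made during exercise: B2 reports that in the previous study blood glucose rose higher and stayed "elevated during exercise despite two to four fold higher insulin concentrations during HA exercise" compared with SL. Followed as written, the plan collects insulin in that window and never compares it between conditions.

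B5.8.2 also does not say which draw is baseline. B5.4 uses the word for the first, fasted sample ("Baseline blood sampling will occur" after an overnight fast), whereas the pre-exercise biopsy pairs with the 300-min draw. If these choices stay open, the time points and the summary measure for insulin can be picked after the data are seen.

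**Working it through.** The check is a count of scheduled draws against the levels of the time factor. B5.8.2 states no figure for this analysis, so there is none to reproduce.

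**1. Exercise window.** B5.3 says: "The drink will be consumed in four boluses throughout the 80-min of steady-state exercise (320, 340, 360, and 380-min"). Exercise lasts 80 min, and B5.4 (Assessment of Urinary Nitrogen Excretion) places the end-of-exercise urine sample at 400 min.

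- Start 320 min; end 320 + 80 = 400 min.
- Draws strictly inside the bout: 340, 360 and 380 min.
- The 420-min draw comes 420 − 400 = 20 min after exercise ends.

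**2. Possible readings of the two levels.** Baseline could be 120, 300 or 320 min; post-exercise could be 400 or 420 min. These give six combinations:

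| Baseline | Post-exercise | Draws left out |
|---|---|---|
| 120 | 400 | 300, 320, 340, 360, 380, 420 |
| 120 | 420 | 300, 320, 340, 360, 380, 400 |
| 300 | 400 | 120, 320, 340, 360, 380, 420 |
| 300 | 420 | 120, 320, 340, 360, 380, 400 |
| 320 | 400 | 120, 300, 340, 360, 380, 420 |
| 320 | 420 | 120, 300, 340, 360, 380, 400 |

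The 340, 360 and 380 min draws are left out in all six. If post-exercise is 420 min, to match the second biopsy, and baseline is 120 or 300 min, neither level is a draw taken during exercise.

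**3. Observations, with 10 completers and two conditions, per analyte.**

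- Scheduled: 8 × 2 × 10 = 160.
- Used by the stated ANOVA: 2 × 2 × 10 = 40, and 40/160 = 25%.
- At 340, 360 and 380 min: 3 × 2 × 10 = 60, and 60/160 = 37.5%.

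**4. Whether another analysis covers these draws.**

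- The paired t-test is limited to turnover and oxidation. In-exercise glucose reaches it indirectly, because the turnover equations in B5.4 use C1 and C2, which "are plasma glucose concentrations at" successive times. Insulin does not enter those equations.
- The post-hoc sentence follows up interactions from the same two-level model.
- The correlation and regression sentence concerns relationships among outcomes, not SL against HA.
- No area under the curve (AUC), peak or multi-level time analysis of insulin appears elsewhere.

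**5. Why one prespecified contrast is better than eight separate tests.** Consider a two-sided paired t-test with n = 10 (9 df) and 80% power. The detectable standardised paired difference d solves: power of a noncentral t with noncentrality d√10 = 0.80.

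- Alpha 0.05: d = 1.00.
- Alpha 0.05/8 = 0.00625: d = 1.43.

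Bonferroni over eight draws is an assumption, since B5.8.2 names no correction method. The comparison supports the form of the fix; it does not estimate harm.

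**The case against.** The strongest reply is that B5.8.2 is a one-paragraph summary, and that the bracketed levels were written with the biopsies in mind while a multi-level factor was intended for blood. A mixed model can take serial draws, and B5.3 calls the draws serial. The paragraph is visibly shorthand: free fatty acids, lactate, glycerol and the catecholamines share the eight-draw schedule, and B5.8.2 names none of them in a test. This may well describe the intent. The text does not say it, though, and glucose and insulin head the list to which the two levels apply. If that was the intent, the same amendment records it.

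A second reply is that 400 min is a fair post-exercise draw, since it marks the end of the bout and falls 20 min after the last bolus. The ANOVA would then compare end-of-exercise insulin. That point stands, so the statement that no level falls within exercise is conditional on the 420-min reading. The omission of 340, 360 and 380 min is not conditional.

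Third, the consequence is limited. The mechanistic aim is exploratory, in-exercise insulin alone cannot separate insulin-dependent from insulin-independent uptake, and GLUT4 staining and Western blots address the question directly at 300 and 420 min, where two levels fit. All of this stands and limits the weight of the point.

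Fourth, eight times by two conditions gives 16 repeated measures on 10 volunteers, and an unstructured covariance would need 16 × 17 / 2 = 136 parameters. A simpler structure has to be chosen. That is routine, and a single summary contrast per volunteer avoids the difficulty.

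**Conclusion.** The concern holds. As written, the ANOVA uses 2 of 8 glucose and insulin draws per protocol day (25% of observations). Insulin at 340, 360 and 380 min (37.5% of observations) has no specified SL–HA test under any choice of baseline and post-exercise draw. The conclusion rests on taking the stated levels of time as the levels of the model, and the counts assume 10 completers with every draw obtained.

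The percentages describe data left out of the test; they do not measure bias or lost power, which cannot be computed without an insulin SD or within-person correlation. The point affects only the exploratory mechanistic aim and leaves the primary oxidation comparison untouched. The plan should be amended because the omitted window is the one that motivates the insulin question and the amendment is cheap.

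**What to change.** Amend B5.8.2 as follows:

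1. Keep the two-level time factor for the biopsy outcomes.
2. For glucose and insulin concentrations, enter all eight Table 3 draws as levels of time in the phase-by-time mixed model, and state the covariance structure.
3. Name the baseline draw for blood: the fasted first draw or the 300-min pre-exercise draw.
4. Prespecify one in-exercise HA–SL contrast for each analyte, for example the mean or AUC over the exercise draws as change from the 300-min draw. The window, including whether 320 and 400 min belong to it, is the investigators' choice but must be fixed before analysis. Draw-by-draw comparisons can follow as descriptive results.

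The cost is SAP wording, slightly more modelling and one more stated contrast. Sampling, assays and the number of volunteers do not change.
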